#### 5.2.1. *Surgery and tumor specimens*

The patient will undergo definitive surgical resection of the primary tumor.

Management of the axilla will be left to the judgment of the surgical oncologist and the patient.

It is strongly preferred that surgery be scheduled between Monday and Thursday for optimal timing of tissue fixation and processing.

The Pathologist will promptly dissect the surgical primary tumor specimen. ASCO-CAP guidelines require initiation of dissection of a surgical specimen within 1 hour of removal from the patient; for this study, minimal “cold ischemia time” is preferred.

The Pathologist will assess whether the tumor specimen is large enough to procure:

- A. tissue for routine diagnostics
- B.  $\geq 8$  core punch biopsies that are 1 mm in diameter and  $\geq 0.5$  cm long for research

C.  $\geq 4$  core punch biopsies that are 3 mm in diameter and  $\geq 0.25$  cm long for research

A 2-cm tumor is expected to provide sufficient material for all needs.

When the tumor is sufficiently large to provide adequate tissue (e.g.,  $>3$  cm), the Pathologist will first remove core punch biopsies for this research study using 1-mm and 3-mm punch biopsy devices. **All research samples must be acquired within 1.5 hours of tissue removal from the patient; a shorter lag time is strongly preferred to maximize tissue viability.** The Pathologist will then acquire tissue samples for routine diagnostics.

If the tumor specimen is approximately 2 cm, the Pathologist may opt to first procure tissue for routine diagnostics. Then if adequate tumor tissue remains to provide punch biopsies for research purposes, these samples will be taken from the tumor. If the tumor is too small to provide adequate tissue for research, the tumor will be considered non-evaluable and the patient will need to be replaced.

Punch biopsy tumor specimens required for this research study are listed below in order of priority.

**A) Fresh tissue (n=8)** - Using a **1-mm** punch biopsy device with plunger (provided by [name]), remove 8 tumor samples  $\geq 0.5$  cm long. These samples will be **immediately** placed into cold (0-4°C) tissue culture medium (serum-free DMEM + Pen/Strep; provided by [name] to be kept on-hand in Pathology lab) and kept on ice or refrigerated (0-4°C). These tissues will be transported **within 30 minutes** of dissection to [name] lab on the 6th floor of Rubin Research Building. [name], [name], and [name] (members of the [name] lab) will be responsible for transporting tissues, and need to be contacted early on the date of surgery with notification that samples will be available the same day. They will be paged when tumor tissues are available for pick-up.

**B) Frozen tissue (n=2)** - Using a **3-mm** punch biopsy device with plunger (provided by [name]), remove 2 tumor samples  $\geq 0.25$  cm long, put into cryotubes (1 core per tube), and snap-freeze in liquid nitrogen. Liquid nitrogen can be provided in a small container by the [name] lab, if they are notified early on the day of surgery.

**C) Formalin-fixed (FFPE) tissue (n=2)** - Using the same **3-mm** punch biopsy device, remove 2 tumor samples  $\geq 0.25$  cm long, fix in formalin (3 hours to overnight), and paraffin-embed the next day as per standard tissue processing procedures in Pathology lab.

Alternatively, if Pathology will be processing diagnostic FFPE tumor samples that will provide sufficient excess tissue for molecular analyses,

and tissues are fixed for less than 24 hours, then such samples may be used in lieu of punch biopsies.

**D) Extra tumor tissue-** If tissue requirements for categories A, B, and C are filled and excess tumor tissue is available, more 1-mm cores of fresh viable tissue for tissue culture are requested (up to 20 more). Such extra cores should be placed into tissue culture medium as in section A (above).

**Histological qualification of tumor samples-** The Pathologist will perform routine histological analysis of the diagnostic FFPE surgical tumor specimen. If the diagnostic tumor sample is found to have <50% tumor cellularity, the tumor samples procured for research will be considered non-evaluable, and this patient will need to be replaced.

#### *5.2.2. Presurgical Letrozole*

Patients enrolled on Arm B will be treated with Letrozole (2.5 mg/day, administered orally) for 10-21 days prior to surgery. This time period has been and continues to be used as a standard time frame in presurgical studies with aromatase inhibitors in patients with ER+ breast cancer. This drug and dose are given as standard adjuvant therapy for up to 5 years following surgical removal of a primary ER+/HER2- breast tumor in patients with Stage I-III disease. The final dose of Letrozole should be taken on the morning of surgery.

It is strongly preferred that surgery be scheduled between Monday and Thursday for optimal timing of tissue fixation and processing.

The primary tumor will be surgically resected as in Section 5.2.1. The Pathologist will promptly dissect the surgical tumor specimen, and obtain punch biopsies for this study as in Section 5.2.1.

#### *5.2.3. Letrozole drug information*

Letrozole (4,4'-(1H-1,2,4-Triazol-1-ylmethylene)bis-benzonitrile) is a synthetic achiral benzyltriazole derivative. It is an orally active highly selective, non-steroidal competitive inhibitor of the aromatase enzyme system (15, 16). Aromatase inhibitors block the aromatase enzyme, consequently lowering estrogen levels and thereby deprive the tumor of its growth stimulus. Letrozole effectively inhibits the conversion of androgens to estrogens in both *in vitro* and *in vivo* (15). This property makes it in particular suitable for postmenopausal women whose main source of estrogen is via peripheral aromatization of androgen precursors.

Preclinical and pharmacodynamic data in humans

*In vivo*, in female rats, the aromatase inhibition manifests itself in a reduction in uterine weight, an increase in body weight, a decrease in serum estradiol concentration, an increase in plasma LH concentration

(16, 17) and suppression of the growth of DMBA-induced rat mammary tumors (15, 18). The ED50 values for some of these effects lie in the range of 0.001 to 0.03 mg/kg with maximal endocrine and anti-tumor efficacy in the dose range of 0.3 to 1.0 mg/kg po (18).

#### Comparison to Aminoglutethimide (AG)

Letrozole is up to 150-250 times more potent than the first generation aromatase inhibitor AG, *in vitro* and more than 10,000 times as potent as AG in inhibiting aromatase *in vivo* (15). The high potency of letrozole is not accompanied by any significant effect on adrenal steroidogenesis *in vitro* or *in vivo* over its maximally effective dose range (16, 17). Inhibition of adrenal steroidogenesis resulting in adrenal hypertrophy does occur with therapeutic doses of AG. The high potency and selectivity of letrozole explains its pharmacological profile and high therapeutic index.

#### Activity in breast cancer patients

In postmenopausal patients with advanced breast cancer, daily doses of 0.1 to 5 mg letrozole suppressed plasma levels of estradiol, estrone and estrone sulfate to 75-95% from baseline (15, 19). Estrogen suppression was maintained throughout the treatment period of 28 days in all patients.

#### Selectivity of letrozole

Letrozole is a highly selective inhibitor of the aromatase enzyme. No clinically relevant changes in the plasma levels of cortisol, aldosterone, 11-deoxycortisol, 17-hydroxyprogesterone, ACTH or plasma renin activity were found in postmenopausal patients treated with a daily dose of letrozole ranging from 0.1 to 5 mg (15, 20, 21). Synacthen tests performed after 6 weeks of treatment with daily doses of 0.1, 0.25, 0.5, 1, 2.5 and 5 mg letrozole indicated no attenuation of aldosterone or cortisol production (22).

#### Toxicities of letrozole

Most adverse reactions to letrozole in the literature are mild to moderate in severity and are indistinguishable from the consequences of the patient's metastatic breast cancer, the effects of estrogen deprivation, or other concurrent illness.

Reported events in greater than 5% of subjects include chest pain, hypertension, edema, hyperlipidemia, cough, dyspnea, nausea, vomiting, abdominal pain, anorexia, increased appetite, constipation, diarrhea, weight gain, weight loss, bone fractures, arthralgias, arthritis, back pain, bone pain, breast pain, myalgias, weakness, asthenia, dizziness, depression, fatigue, headache, insomnia, lethargy, malaise, rash, hot flashes, sweats, vaginal bleeding, vaginal dryness, and infections.

Letrozole will be prescribed by the subject's oncology provider and the subject will be asked to fill the prescription at her commercial pharmacy.

### 5.3 Study exit

Following surgery, the patient's role in the study will end. The patient will then be treated as per standard-of-care by her treating oncologist. Subjects who begin letrozole in the pre-surgical setting may receive chemotherapy followed by resumption of letrozole or letrozole alone following the definitive surgical resection.

### 5.4. Evaluable patients

Subjects who proceed to a definitive surgical procedure with A) tumor tissue sufficient to provide punch biopsy specimens for research purposes, and B) histologically-confirmed tumor tissue in the surgical specimen with  $\geq 50\%$  tumor cellularity, will be considered evaluable. Subjects whose surgical specimens do not contain adequate tumor tissue to assess the primary endpoint will not be considered evaluable, and will need to be replaced.

### 5.5. Analyses

#### 5.5.1. *Ex vivo analysis of RAD001 effects on IRS-1/PI3K/AKT signaling.*

Fresh viable tumor cores in tissue culture medium (serum-free DMEM + Pen/Strep) will be placed into medium containing 20 nM RAD001 (4 cores) or DMSO control (4 cores) and cultured at 37°C for 1 hour. If extra tissue cores are available, we will treat +/- 20 nM RAD001 for 2-8 hours to evaluate delayed changes in signaling, and treat +/- 1 uM OSI-906 (IGF-1R/InsR inhibitor) for 1-8 hours to determine whether PI3K/AKT signaling is IGF-1R/InsR-dependent in these tumors. Tissue cores will then be snap-frozen in liquid nitrogen and stored at -80°C.

Immunoblotting- Two cores each of DMSO- and RAD001-treated tumor will be homogenized and lysed on ice in RIPA buffer containing protease and phosphatase inhibitors. Samples will be sonicated and centrifuged, and supernatant will be used to quantify protein concentration. Protein lysates for immunoblotting will then be mixed with reducing sample buffer and stored at -80°C. Lysates will be heated at 95°C for 1 min. just before SDS-PAGE following by immunoblot analysis using antibodies against:

IRS-1

phospho-IRS-1-Ser636/639 (marker of p70S6K activity)

IRS-2

AKT

phospho-AKT-S473 (marker of mTORC2 activity)

phospho-AKT-T308 (marker of PIP3 levels and PI3K/PDK1 activity)

4E-BP1

phospho-4E-BP1-Thr37/46 (marker of mTORC1 activity)

p70S6K  
phospho-p70S6K-Thr389 (marker of mTORC1 activity)  
S6  
phospho-S6-Ser240/244 (marker of p70S6K activity)  
phospho-S6-Ser235/236 (marker of p70S6K and RSK activity)  
Erk1/2  
phospho-Erk1/2-Thr202/Tyr204 (marker of MEK activity)  
IGF-1Rb  
InsRb

If excess protein lysate is available, we will immunoprecipitate the p85 subunit of PI3K, and immunoblot for IRS-1 and IRS-2 to assess drug induced changes in IRS-1/2-induced PI3K activation. We will also immunoprecipitate using phospho-Tyrosine antibody, and immunoblot for IGF-1Rb, InsRb, IRS-1, and IRS-2 to assess protein activation.

The primary goal of this analysis is to determine whether RAD001 treatment *ex vivo* globally decreases mTORC1 signaling (indicated by a decrease in levels of phospho-p70S6K, phospho-S6, and phospho-4E-BP1), increases IRS-1/2 levels and phosphorylation, and increases AKT phosphorylation. Secondary goals are to assess changes in IGF-1R and InsR activation, and compensatory signaling through the MEK/Erk pathway.

Immunohistochemistry (IHC) on frozen tissues- Two cores each of DMSO- and RAD001-treated tumor will be sectioned and processed for IHC in the Pathology Translational Research Shared Resource. Tissue sections will be immunostained using antibodies against phospho-S6-Ser240/244, phospho-AKT-S473, phospho-AKT-T308 and phospho-IGF-1Rb/InsR- Tyr1131/Tyr1146. Samples will be scored using a Histoscore scale that incorporates staining intensity and frequency (12).

The primary goal of this analysis is to determine whether RAD001 treatment *ex vivo* decreases mTORC1 signaling (indicated by a decrease in levels of phospho-S6) and increases AKT phosphorylation uniformly throughout tumor cores, and whether drug treatment alters IGF-1R/InsR phosphorylation (which cannot be assessed by immunoblot analysis of protein lysates). Staining intensities in the center of each core will be compared to the outer edges to assess uniformity of signal; non-uniformity may be due to time of exposure of cells to drug or medium.

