alter IRS-1/PI3K/AKT pathway activation in breast tumors. RAD001-induced pathway activation will be defined as a  $\geq 50\%$  increase in phospho-AKT densitometric signal value compared to DMSO-treated control; this scoring system provides a binary metric for sample size determination for Arm B (below). Given that this is a pilot study, we do not know what fraction of ER+/HER2-breast tumors will exhibit RAD001-induced IRS-1/PI3K/AKT activation. Hence, tumors from 10 untreated patients in Arm A will be used to determine the frequency with which RAD001 induces AKT activation.

The fraction of tumors in Arm A (untreated patients) that exhibit RAD001-induced AKT activation will be used to determine the number of patients that need to be enrolled in Arm B (presurgical Letrozole treatment) to detect a significant effect of presurgical Letrozole treatment on RAD001-induced AKT activation. We estimate that  $\leq 15\%$  of Letrozole-treated tumors will exhibit RAD001-induced AKT activation. If we observe that RAD001 increases phospho-AKT in X of 10 tumors in Arm A, we will enroll Y patients in Arm B (presurgical Letrozole) to provide a sufficient number of tumors to detect a significant effect ( $p \leq 0.05$ ) of presurgical Letrozole on RAD001-induced changes in phospho-AKT levels with 80% power (calculated using uncorrected chi-squared statistic). If we observe that  $\leq 3$  tumors from untreated patients in Arm A exhibit RAD001-induced AKT activation, the study will be terminated at this point, and Arm B will not enroll patients. To account for interpatient/intertumor variability, we will enroll a minimum of 10 patients in Arm B.

X (n of tumors from untreated patients that exhibit a <math>\geq 50\%</math> increase in P-AKT levels in response to RAD001 treatment ex vivo)	Y (n of patients to be enrolled in Arm B, presurgical Letrozole)
0-3	Terminate study
4-6	30
7-8	14
9-10	10

- 10.

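### The plan does not specify how cores are assigned to RAD001 or DMSO, or whether the densitometry reader is masked, yet a 50% cut on that readout decides whether Arm B opens and how large it is.

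*Combined protocol and SAP*

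**What the plan says.** - **Collection (5.2.1, item A).** Pathology is to "remove 8 tumor samples" with a 1-mm punch. Core length, medium, temperature and transport time are given. Recording of punch position or order is not requested.
- **Exposure (5.5.1).** Cores "will be placed into medium containing 20 nM RAD001 (4 cores) or DMSO control (4 cores"). No rule says which core goes where.
- **Immunoblot (5.5.1).** "Two cores each of DMSO- and RAD001-treated tumor will be homogenized and lysed on ice in RIPA buffer". Two further cores per condition go to immunohistochemistry (IHC). How the four are divided between the assays is not stated.
- **IHC reading (5.5.1).** "Samples will be scored using a Histoscore scale that incorporates staining intensity and frequency". Masking is not mentioned for this or for densitometry.
- **Coding (6.1, 10.4).** Specimens carry a code or case number. The purpose is confidentiality; nothing there hides drug condition from a reader.
- **Analysis (9.3).** RAD001 and DMSO values are compared by a paired t-test within tumor, separately by arm. The size of the change is then compared between arms.
- **Gate (9.6).** Activation is a rise of at least 50%, defined as an "increase in phospho-AKT densitometric signal value compared to DMSO-treated control"; "this scoring system provides a binary metric for sample size determination for Arm B (below"). Also, "tumors from 10 untreated patients in Arm A will be used to determine the frequency with which RAD001 induces AKT activation". With 3 or fewer activated tumors, "the study will be terminated at this point, and Arm B will not enroll patients". Otherwise X of 4-6, 7-8 or 9-10 sets Arm B at 30, 14 or 10.

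**The concern.** The RAD001 versus DMSO contrast is an experiment within each tumor, and the investigators control which core gets which treatment. Two safeguards are normal for such an experiment, and the plan provides for neither.

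The first is assignment. If the RAD001 and DMSO cores come from different parts of a tumor, a difference between regions enters the ratio. The plan itself expects signal to vary within a core: 5.5.1 compares centre with edge and names exposure time to drug or medium as a possible cause.

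The second is masking. Densitometry involves judgement over band limits, background and exposure. The expected direction is stated in advance: activation by RAD001 (1.4), and in at most 15% of Letrozole-treated tumors (9.6). Because the arms run one after the other, a reader could expect activation in Arm A and little in Arm B.

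The readout rests on two cores per condition and is dichotomised. One or two miscalled tumors can move X to another row of the table. A wrongly opened Arm B would enrol 10 to 30 women in a study that 10.3 says offers them no direct clinical benefit. A wrongly closed one would lose the second primary objective.

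**Working it through.** **The plan's own figure.** Taking Arm A as 10, the Arm B rate as 15%, and an uncorrected two-sided test at 0.05, power at the tabulated Arm B size is 40%, 60% and 79% at X = 4, 5 and 6 (Y = 30); 82% and 94% at X = 7 and 8 (Y = 14); 98% and over 99% at X = 9 and 10 (Y = 10). The shortfall at X = 4 and 5 is a separate matter that assignment and masking do not affect. What matters here is that X picks the row.

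**Inputs from the plan.** Cut at a ratio of 1.5, so ln 1.5 = 0.405; two blotted cores per condition; 10 tumors; Arm B opens at X of 4 or more.

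**Inputs assumed, because the documents give none.** One phospho-AKT ratio per tumor, normal on the log scale; two cores averaged per condition; per-core log SD s = 0.3; region log SD r = 0.2 to 0.4, mean zero; a reading tilt of 10% toward RAD001.

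**Formulas.** Core noise contributes s²/2 + s²/2 = s² to the variance of the log ratio. Region adds:
- nothing if the blotted cores are position-matched pairs, because it cancels;
- r²/2 + r²/2 = r² if each core has its own independent region value (haphazard picking);
- 2r² if each condition comes wholly from one region.

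For a true ratio e and tilt t, q = 1 − Φ[(0.405 − ln(e·t)) / SD], and P(X ≥ 4) is the binomial upper tail with n = 10.

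**Assignment, no drug effect (e = t = 1).**

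| Assignment | r | SD of log ratio | q per tumor | P(X ≥ 4) |
|---|---|---|---|---|
| Matched pairs | any | √0.09 = 0.300 | 8.8% | 0.8% |
| Haphazard | 0.2 | √(0.09 + 0.04) = 0.361 | 13.0% | 3.2% |
| Haphazard | 0.4 | √(0.09 + 0.16) = 0.500 | 20.9% | 13.7% |
| One region each | 0.2 | √(0.09 + 0.08) = 0.412 | 16.3% | 6.5% |
| One region each | 0.4 | √(0.09 + 0.32) = 0.640 | 26.3% | 25.6% |

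**Pairing at treatment only.** Suppose pairs are split between conditions but the blotted cores are then chosen without regard to pair. The two blotted RAD001 cores share 0, 1 or 2 pairs with the two blotted DMSO cores with probability 1/6, 4/6 and 1/6, and the region variance is r², r²/2 or 0. Averaging gives q of 11% to 16% and P(X ≥ 4) of 2% to 6%. The 0.8% is reached only if both members of a pair go to the same assay.

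**Reading tilt (SD 0.3, t = 1.10).**

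| True rise | q without → with tilt | P(X ≥ 4) without → with tilt |
|---|---|---|
| None | 8.8% → 15.1% | 0.8% → 5.1% |
| 30% | 31.7% → 43.7% | 40% → 70% |
| 60% | 58.5% → 70.3% | 93% → 99% |
| 100% | 83.1% → 89.9% | over 99.9% both ways |

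**Larger noise.** With no drug effect and no tilt, P(X ≥ 4) is 0.8%, 5.6% and 13.7% at log-ratio SD 0.3, 0.4 and 0.5. A consistent 10% shift makes these 5%, 16% and 27%. The part present without a shift is ordinary core and blot noise, which neither safeguard removes.

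**The case against.** The case against has several parts.

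- **Silence is not a statement.** A reader might infer that cores are assigned non-randomly and blots read unmasked. The documents say neither; they do not address it. The laboratory may already code its lanes. This stands, and the point is worded accordingly. But 5.2.1 and 5.5.1 specify punch size, temperature, buffer and antibodies, and nothing in the plan would lead the laboratory to randomise, match or mask.
- **Histoscores.** A reader might infer that unmasked slide scoring could also push a tumor over the 50% line. It cannot: 9.6 defines the line by densitometry alone, as 9.1 defines the primary endpoint. Masking of Histoscores matters for the IHC readout and the secondary analyses in 9.4.
- **Noise is not bias.** A reader might infer that region differences bias the first primary objective. If they vary in sign from tumor to tumor, the paired t-test absorbs them as variance, so they cost precision. Bias would need a pattern repeated across tumors, such as punch order tied to condition, and none is documented. The count X is different: it registers only rises, so when the true effect lies below the line, even zero-mean noise adds activations.
- **Delay in medium.** Cores go straight into cold medium and reach the laboratory within 30 minutes of dissection, so time in medium is weak grounds for a systematic difference. This stands.
- **The sizes depend on the inputs.** The move from 40% to 70% needs a true rise just under the cut; elsewhere the same tilt matters much less. This stands too.
- **It is a pilot.** True, but this pilot's count decides whether more patients are enrolled.

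**Conclusion.** The concern holds in limited form. Assignment of cores to condition, matching by position, choice of blotted cores, and masking of densitometry are not specified, and the resulting phospho-AKT ratio governs whether Arm B opens and its size.

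Two effects should be kept apart. Region differences inflate the count of activated tumors when the true effect is below 50%, but leave the paired t-test unbiased if their mean is zero. Unmasked reading could bias both the count and the t-test.

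With no drug effect and the assumed SDs, false activation per tumor is about 9% with matched pairs, 13% to 21% with haphazard picking, and 16% to 26% with one region per condition; the last is a worst case, not a description of what the plan prescribes. The effect of a 10% tilt on the gate ranges from negligible at a doubling to 30 percentage points at a true 30% rise. All of these figures are illustrations on assumed SDs and tilts, not estimates for this trial. The case for change rests on the role of the cut and the low cost of the remedy.

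**What to change.** In 5.2.1 and 5.5.1:

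1. Take the 8 fresh cores as 4 adjacent pairs.
2. From a pre-printed random list, assign one core of each pair to RAD001 and the other to DMSO.
3. From the same list, send two whole pairs to immunoblot and two whole pairs to IHC, so that region cancels in the blotted ratio.
4. Label tubes, lanes and slides with random codes. Another current laboratory member holds the key.
5. Quantify and lock phospho-AKT densitometry under code before mTORC1 markers such as phospho-S6 are read. RAD001 lowers phospho-S6, so seeing it could reveal the condition.
6. Unmask after the values are locked and before X is counted.
7. Score Histoscores under code as well, for the IHC and secondary analyses.

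Apply the same procedure in Arm B, so that the between-arm comparison in 9.3 is protected.

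The cost is a few minutes of labelling per specimen and a fixed reading order. No extra patients, tissue, assays or staff are needed, and no sample size changes.
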